6.4. Vital Signs and Weight

Extreme vital signs will be determined using the following criteria:

- Pulse rate either < 50 bpm or > 100 bpm,
- Systolic blood pressure either ≤ 90 mmHg or ≥ 160 mmHg,
- Diastolic blood pressure either ≤ 50 mmHg or ≥ 100 mmHg.

The number (percent) of patients having extreme vital signs will be tabulated by treatment group at each scheduled visit. The percentage will be calculated using the number of patients in the Safety population with data at each visit as the denominator. The number (percent) of patients having extreme vital signs post-baseline (including unscheduled assessments) will be calculated.

Change from baseline statistics will also be defined for the measurements of blood pressure, pulse rate and temperature using the pre-dose values as baseline. Descriptive statistics for the measurement of temperature will also be provided by treatment group.

All patients who have an extreme vital sign value will be documented in a by-patient listing. The listing will include all of the vital sign measurements from the study for the patient, and the noteworthy values will be flagged.

6.5. Electrocardiograms

At each time point, the change from baseline will be derived for each numeric parameter using the pre-dose value as baseline. Descriptive statistics for the value of each parameter at each time point and the change from baseline for each parameter at each post-dose time point will be provided by treatment group.

The number (percent) of patients who either had an abnormal ECG (regardless whether clinically significant or not) or had an extreme QTc value at any time while on-treatment will be tabulated by treatment group. Extreme QTc values will be determined using the following criteria:

- QTc \geq 500 msec
- QTc \geq 550 msec
- Change from baseline in QTc \geq 30 msec
- Change from baseline in QTc \geq 60 msec.

All on-treatment values, including unscheduled assessments, will be considered.

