 - Positive QuantiFERON®-tuberculosis test at screening AND have not been vaccinated for tuberculosis. If result is indeterminate, a single retest will be allowed. If the result of the second test is still indeterminate, the subject will be excluded. Patients who have been vaccinated with BCG at any time in the past do NOT need to undergo testing. Documentation of previous vaccination is required.
 - For women, positive serum pregnancy test.
 - Evidence of HIV infection or are positive for HIV antibodies based on history or point-of-care testing (POCT) at screening

- Positive test for active hepatitis B as defined as:
 - Positive for hepatitis B surface antigen (HBsAg), or
 - Positive for anti-hepatitis B core antibody (HbcAb) and positive for hepatitis B deoxyribonucleic acid (HBV DNA).
- Positive of anti-hepatitis C antibody with confirmed presence of hepatitis C virus by RNA testing, or chronic liver disease with the most recent available aspartate transaminase (AST) or alanine transaminase (ALT) $> 2 \times$ the upper limit of normal (ULN).
- Evidence of clinically significant hepatic or renal impairment, including ALT above $2 \times$ ULN, AST above $1.5 \times$ ULN, total bilirubin (TBL) above $2 \times$ ULN (TBL accepted up to $2 \times$ ULN if direct bilirubin is within normal limits), or estimated glomerular filtration rate (eGFR) < 60 mL/min/1.73m² (based on CKD-EPI calculation method).

17. Clinically significant ECG abnormalities at screening, or clinically significant personal or family history (in a first-degree relative) of heart diseases, including:

- Confirmed corrected QT (QTcF) interval > 450 msec for both men and women.
- Bundle branch blocks and other conduction abnormalities other than:
 - mild first degree atrioventricular block (≤ 205 msec) or
 - QRS duration shorter than 110 msec without bundle branch block morphology.
- Irregular rhythms other than sinus arrhythmia or occasional, rare supraventricular ectopic beats.
- History of unexplained syncope.
- Family history of unexplained sudden death or sudden death due to long QT syndrome.

18. Are receiving any of the following therapies for psoriasis:

- Systemic retinoids within 12 weeks prior to dosing in this study;

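### SAP 6.5, and to a lesser extent 6.4, counts abnormal ECGs and extreme vital signs without regard to baseline, which dilutes any contrast in new findings; no category shows absolute QTc level below 500 msec (minor priority)

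*SAP*

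**What the plan says.** **ECG.** For each arm, over the whole treatment period, SAP 6.5 plans this count: "The number (percent) of patients who either had an abnormal ECG (regardless whether clinically significant or not) or had an extreme QTc value". It adds: "All on-treatment values, including unscheduled assessments, will be considered". The extreme-QTc criteria are absolute values of at least 500 and at least 550 msec, and rises from baseline of at least 30 and at least 60 msec. The SAP writes QTc without naming a correction formula. SAP 6.5 also summarises each numeric ECG parameter and its change from baseline at each time point; under SAP 8 these summaries include the maximum.

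**Vital signs.** SAP 6.4 states: "The number (percent) of patients having extreme vital signs post-baseline (including unscheduled assessments) will be calculated". It also plans extreme values by group at each scheduled visit, change-from-baseline statistics, and a listing of all vital-sign measurements for every flagged patient.

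**Entry.** Protocol 6.2, criterion 17, excludes clinically significant ECG abnormalities. It tolerates some minor ones, among them "mild first degree atrioventricular block", sinus arrhythmia and rare supraventricular ectopic beats. Its QT exclusion reads: "Confirmed corrected QT (QTcF) interval > 450 msec for both men and women". The exclusion criteria set no numeric limit on pulse or blood pressure.

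**Elsewhere in the SAP.** Adverse events are restricted to those that begin or worsen after the first dose (SAP 6.2), and laboratory data get pre-dose to post-dose shift tables (SAP 6.3.2). Safety endpoints are not tested (SAP 6).

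**The concern.** A patient who enters with an admitted minor ECG abnormality and shows the same tracing on treatment is counted as abnormal on treatment. Nothing else planned in SAP 6.5 undoes this. The change-from-baseline summaries cover numeric parameters, whereas normal/abnormal is a category, and the section names no ECG shift table, no by-visit abnormal count and no listing of flagged patients. The SAP separates new from pre-existing findings for adverse events and laboratory data, but not here.

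The any-time vital-sign count has the same form. It is post-baseline rather than on-treatment, so it spans nine scheduled visits (Weeks 1, 2, 4, 8, 12, 14, 16, 18 and 20), the last four after dosing has ended.

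For QTc, entry is capped at 450 msec and the lowest absolute row is 500 msec, so the categories carry no information on absolute level in between.

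Safety and tolerability is a secondary objective. With about 27 patients per arm and no testing, readers will judge these tables by eye, so what the counts contain matters.

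**Working it through.** The plan states no figure for this point, so there is none to reproduce. Two checks apply.

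**1. Dilution of the abnormal-ECG count**

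Inputs:
- About 27 patients per arm (SAP 1.3).
- Share abnormal at baseline, *b*: not in the documents, so varied from 0% to 50%, with every such finding assumed to persist on treatment.
- New-onset rates among patients normal at baseline: not in the documents; assumed 5% on placebo and 25% on active.

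Rate shown by the planned count = *b* + (1 − *b*) × new-onset rate. At *b* = 20%:
- placebo: 0.20 + 0.80 × 0.05 = 24.0%
- active: 0.20 + 0.80 × 0.25 = 40.0%
- ratio: 40.0 / 24.0 = 1.7

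Counting only patients normal at baseline keeps 5% against 25%, a ratio of 5.0, at every *b*. The last two columns give the exact power of a one-sided 10% Fisher test, as a yardstick only. The baseline-normal column uses 27 × (1 − *b*) patients per arm, rounded.

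| *b* | Planned count, placebo vs active | Ratio | Yardstick power, planned count | Yardstick power, baseline-normal only |
|---|---|---|---|---|
| 0% | 5.0% vs 25.0% | 5.0 | 0.70 | 0.70 |
| 10% | 14.5% vs 32.5% | 2.2 | 0.48 | 0.65 |
| 20% | 24.0% vs 40.0% | 1.7 | 0.37 | 0.60 |
| 30% | 33.5% vs 47.5% | 1.4 | 0.32 | 0.52 |
| 50% | 52.5% vs 62.5% | 1.2 | 0.22 | 0.33 |

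The expected difference in number of patients is the same either way; the noise around it differs. Take *b* = 20% and a smaller assumed effect, 5% against 15%:
- Planned count: rates 24% and 32%. Expected difference 27 × 0.08 = 2.2 patients; SD = √[27 × (0.24 × 0.76 + 0.32 × 0.68)] = √10.8 = 3.3.
- Baseline-normal only, 27 × 0.80 = 21.6 per arm: expected difference 21.6 × 0.10 = 2.2 patients; SD = √[21.6 × (0.05 × 0.95 + 0.15 × 0.85)] = √3.78 = 1.9.

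**2. What the QTc categories show**

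From a baseline of at most 450 msec:
- Reaching 500 needs a rise of at least 500 − 450 = 50 msec.
- Reaching 480 needs a rise of at least 480 − 450 = 30 msec, so every such patient is already in the 30 msec row.
- A value of 451-479 msec reached with a rise under 30 msec is in no category. Example: 445 to 474 is a rise of 29.
- Level is not distinguished within the change rows. A move from 390 to 420 (rise 30) and one from 448 to 498 (rise 50) fall in the same row: at least 30, below 60, below 500.

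One qualification: the 450 cap applies to QTcF at screening, while SAP 2.5 takes the last value on or before Day 1 as baseline. A baseline above 450 is therefore possible.

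**The case against.** The case for leaving the plan alone has real weight.

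- **Moderate QTc prolongation.** A reader might infer that the tables miss it. They do not. The 30 and 60 msec rows count it, and the by-visit summaries include the maximum. Only the absolute level below 500 msec is missing from the categories. This objection stands.
- **Swamping of drug effects.** A reader might also infer that pre-existing findings overwhelm any drug effect. No figure in the documents supports that. Criterion 17 removes clinically significant abnormalities, randomisation spreads the remaining minor ones over placebo and active alike, and at 0% prevalence nothing is lost. This stands as to size. It does not remove the dilution, because balance on average does not restore the contrast.
- **Vital signs.** The by-visit table, on its wording, covers screening and Day 1, so baseline frequency by arm can be read from it; change from baseline and a full listing are also planned. This largely stands. What remains is that the any-time count does not pair patients with their own baseline.
- **Clinically significant findings.** Those from ECGs and vital signs after the first dose are reported as adverse events (Protocol 9.4.1 and 9.4.2), and the safety endpoint is treatment-emergent adverse events. This stands, and it lowers the priority.
- **Sample size.** With 27 per arm, chance matters whichever count is used. True, but in the example above the baseline-aware count cuts the SD from 3.3 to 1.9 patients for the same expected difference.
- **Unseen shells.** Table formats are in a companion document (SAP 1.1), so separate rows or a baseline column may exist there. That cannot be judged from the SAP text.

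**Conclusion.** The point holds as a minor improvement, chiefly to the ECG table. As written, the SAP 6.5 abnormal-ECG count mixes new and pre-existing findings, and nothing else in that section separates them. Dilution is the supportable description. Its size rests on a baseline prevalence that the documents do not give and on assumed new-onset rates: with 5% against 25%, the ratio stays at 5.0 if no patient is abnormal at baseline, and falls to 1.7 at 20% prevalence and 1.2 at 50%. The vital-sign gap is confined to the any-time post-baseline count. For QTc, rises of 30 msec or more are already counted; the categories lack absolute level below 500 msec, and the SAP does not say which correction it uses although the protocol's limit is in QTcF. No formal inference depends on these tables.

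**What to change.** In SAP 6.5:
- Add a baseline-to-worst-on-treatment ECG shift table, or count an abnormal ECG only when it is new or worsened from baseline.
- Tabulate this separately from the QTc criteria.
- Name QTcF as the correction, matching criterion 17.
- Add absolute rows for >450 and >480 msec to the existing rows. The >480 row shows level only and adds no new patient whose baseline is at or below 450.

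In SAP 6.4, beside the any-time post-baseline count, give the number of patients whose extreme value was not present at baseline.

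The cost is SAP and table-shell wording plus a little programming. Baseline and on-treatment ECGs and vital signs are already in the schedule, and no procedure, visit or clinical rule changes.

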6.6. Other Safety Analyses

Results of physical exams will be included in listings but not summarized.

7. PHARMACOKINETIC/PHARMACODYNAMIC ANALYSES

Pre-dose samples are to be obtained at 1 week, 2 weeks, 4 weeks and 8 weeks after the first dose of study drug. On the last day of dosing (Day 85/Week 12), the following samples are to be collected: pre-dose and 1, 2, 4, 8, 24 (Day 86), 72 hr (Day 88), and 168 hr (1 week; Day 92) post dose. One sample should be taken at the EOS visit (at least 6 weeks after the last dose [Week 18]). One sample should be taken at the early termination visit, if applicable.

Pharmacokinetic parameters will be summarized by dose level using descriptive statistics. PK parameters such as the maximum concentration (C_{max,ss}), time of maximum concentration (T_{max,ss}), area under the concentration versus time curve within a dosing interval (AUC_{0- τ ,ss}), the first-order terminal elimination rate constant (λ_z), the terminal elimination half-life (t_{1/2}), apparent clearance (CL/F), and apparent volume of distribution (V_d/F) will be reported. Other parameters may be calculated as deemed appropriate. Mean and individual PRCL-02 plasma concentration-time curves will be represented graphically.

Note that for all PK parameters but T_{max}, summary statistics will include geometric mean and geometric CV%. T_{max} will be reported as median and range (minimum to maximum).

The PK/PD relationship of PRCL-02 with PD, efficacy, and/or safety measures may be explored.

8. REPORTING CONVENTIONS

This section details the general conventions to be used for the statistical analyses. Departures from these general conventions will be provided in the specific detailed sections of this analysis plan. The following conventions will be applied to all data presentations and analyses:

- Quantitative variables will generally be summarized by the number of patients, mean, standard deviation, median, minimum, and maximum.
- Categorical variables will be summarized by the number and percentage of patients within each category.
- All mean and median values will be formatted to one more decimal place than the measured value.

- Standard deviation values will be formatted to two more decimal places than the measured value.
- Minimum and maximum values will be presented with the same number of decimal places as the measured value.
- The number and percent of responses will be presented in the form XX (XX %), where the percentage is in parentheses. Percentages will be rounded to the nearest percent. In the case of a frequency of zero, the frequency and percentage will be presented as 0 rather than 0 (0%).
- All summary tables will include the analysis population sample size (i.e. number of patients) in each treatment group.
- Date variables will be formatted as ddMMYY for presentation.

For PK data, the geometric coefficient of variation will be calculated assuming the data follow a log-Normal distribution. That is, let X = concentration.

If $Y = \log[X]$ has a Normal distribution with

$$E[Y] = \mu \text{ and } \text{Var}[Y] = \sigma^2,$$

then X has a log-Normal distribution with

$$E[X] = \exp[\mu + .5*\sigma^2] = \exp[\mu]*\exp[.5*\sigma^2]$$

and

$$\text{Var}[X] = \exp[2\mu + 2*\sigma^2] - \exp[2\mu + \sigma^2] = \exp[2\mu]*\exp[\sigma^2]*(\exp[\sigma^2] - 1)$$

so

$$\text{SD}[X] = \exp[\mu]*\exp[.5*\sigma^2]*\sqrt{\exp[\sigma^2] - 1}$$

Therefore, $CV[X] = \text{SD}[X]/E[X] = \sqrt{\exp[\sigma^2] - 1}$. The log-transformed concentration values will be computed and the coefficient of variation calculated using the sample variance.

9. SCHEDULE OF ASSESSMENTS

Procedure	Screening									FU	EoS
Visit #	1	2	3	4	5	6	7	8	9	10	11
Study Days	-28 to -1	1	8	15	29	57	85	99	113	127	141
Window Period (Days)		±2	±2	±2	±2	±2	±2	±2	±2	±2	±2
Week	-	-	1	2	4	8	12	14	16	18	20
Informed consent	X										
Demographics	X										
Medical history	X										
Inclusion and exclusion criteria	X	X									
Pregnancy test (♀)	X	X	X	X	X	X	X	X	X	X	
Serum FSH (PMP ♀)	X										
QuantiFERON TB Test		X									
HIV/hepatitis screen	X										
Randomization		X									
Study drug dispensing		X	X	X	X	X					
Study drug accountability			X	X	X	X	X				X if ET
Safety Evaluations											
Physical examination	X	X	X	X	X	X	X				X
Height/weight	X	X	X	X	X	X	X				X
Vital signs (pulse and BP)	X	X	X	X	X	X	X	X	X	X	X
12-lead ECG	X	X	X	X	X	X	X				X
Clinical laboratory tests	X	X	X	X	X	X	X				X
AE monitoring	X	X	X	X	X	X	X	X	X	X	X
Concomitant medications	X	X	X	X	X	X	X	X	X	X	X
Efficacy and Other Evaluations											
PASI	X	X	X	X	X	X	X	X	X	X	X
sPGA	X	X	X	X	X	X	X	X	X	X	X
PK sampling			X	X	X	X	X	X	X	X	X
Plasma sample collection for PGx assessments		X									

See protocol for footnotes.
